9.1.3. Analysis of Safety

Analysis of safety data will be presented for all subjects in the Safety population (i.e., all subjects receiving randomized study product). AEs will be coded using Medical Dictionary for Regulatory Activities (MedDRA, most current version) and categorized by system organ class using preferred terms. AEs will be tabulated by study group with respect to their intensity and relationship to the study product. Ophthalmoscopy findings will be summarized descriptively. IOP measurements, Snellen Distance VA by pinhole method and Slit Lamp Biomicroscopy will be summarized as safety outcomes.

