3.2. DESCRIPTION OF STUDY AND DURATION OF PARTICIPATION

3.2.1. Description of Trial Design

This is a Phase III, multicenter, double-masked, randomized, placebo-controlled, parallel-group study designed to evaluate the efficacy and safety of two doses and two dosing regimens of KPI-121 versus placebo in subjects who require treatment of postoperative anterior ocular inflammation. Approximately 500 subjects will be screened and up to 402 subjects with one study eye each randomized in this study at approximately 25 centers located in the US. Subjects who experience postoperative inflammation on the first day following routine, uncomplicated, cataract surgery and who meet all other eligibility criteria will be randomized to one of four study groups in an approximate 2:2:1:1 ratio:

- KPI-121 0.25% QID
- KPI-121 1.0% BID
- Placebo A QID
- Placebo B BID

Dosing of study product will be initiated on the day following surgery and instilled as one to two drops in the study eye according to the assigned dosing regimen for 14 days. The first dose of study product will be administered by the subject under the supervision of a designated study team member who is otherwise uninvolved in the assessment or evaluation of the subject. Except for this study product administration, no other information or discussion regarding the subject's assigned study product or regimen will be exchanged, in order to maintain the masking for this trial.

This study will include up to 7 clinic visits (including the surgery day) over 18 to 33 days total study duration. Visit 1 (Screening) will occur between 14 to 1 day(s) prior to surgery and subjects who meet preoperative screening inclusion/exclusion criteria will be entered into the study. At Visit 2 (Surgery/Day 0), subjects will undergo routine cataract surgery according to the Investigator's normal procedures. Visit 3 (Randomization/Day 1) will occur on the day following surgery. Subjects who meet the qualifying postoperative randomization criteria will be eligible for randomization to one of the four study groups and will initiate study product on that day. Following randomization, subjects will be instructed to return to the clinic to be evaluated at Visit 4 (Day 4 \pm 1 day), Visit 5 (Day 8 \pm 1), and Visit 6 (Day 15 \pm 1). The last dose of study product will be administered upon completion of 14 days of evaluation. Following

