4.2. SUBJECT EXCLUSION CRITERIA

In order for subjects to be eligible at Visit 1 they may not:

1. Require concurrent ocular therapy (either eye) with nonsteroidal anti-inflammatory drugs (NSAIDs), mast cell stabilizers, antihistamines, or decongestants within 2 days prior to surgery and for the duration of the study.
2. Require treatment with systemic NSAIDs, with the exception of ≤ 81 mg/day of acetylsalicylic acid (ASA or aspirin), for the duration of the study
3. Require treatment with systemic (except stable maintenance dose of inhaled or intranasal corticosteroids) or ocular (either eye) corticosteroids (other than study product) within 14 days prior to cataract surgery and for the duration of the study
4. Require concurrent ocular therapy with immunosuppressants (e.g., Restasis[®]) within 30 days prior to surgery and for the duration of the study.
5. Require change in treatment with anticholinergics, systemic immunosuppressive agents, oral steroids (dose must be less than 11 mg/day) within six months prior to Visit 1.
6. Require change in stable treatment with antidepressants within 6 months prior to Visit 1.
7. Require change in use of nutraceuticals or multivitamins during trial participation.
8. Have known hypersensitivity or contraindication to the study product(s) or their components.
9. Use any topical ophthalmic medications including glaucoma medications, all eye drops (except antibiotic eye drops considered to be included in post cataract surgery standard of care treatment), all gels or artificial tears within 2 days prior to surgery and for the duration of the study.
10. Use any topical eyelash growth medications within 7 days prior to surgery and for the duration of the study
11. Use TNF-blocking agents (e.g., etanercept, adalimumab, infliximab) within two days prior to surgery and for the duration of the study
12. Have history of glaucoma, IOP >21 mmHg at the screening or randomization visit(s), or are being treated for glaucoma in either eye.
13. Wear contact lenses for 4 weeks prior to Visit 1 and throughout the study.

14. Be monocular or have Snellen Distance VA by pinhole method of 20/200 or worse in the non-study eye.
15. Have had penetrating intraocular surgery in the study eye within 3 months or within two weeks in the fellow eye.
16. Have had selective laser trabeculoplasty (SLT) within 3 months prior to surgery.

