8.2. ADVERSE EVENT DEFINITIONS

Adverse Event (AE): Any untoward medical occurrence associated with the use of an investigational product in humans, whether or not considered drug related.

Adverse Reaction (AR): any AE caused by a drug. Adverse reactions are a subset of all suspected adverse reactions where there is reason to conclude that the drug caused the event.

Suspected Adverse Reaction (SAR):

Any AE for which there is a reasonable possibility that the drug caused the AE. For the purposes of IND safety reporting, “reasonable possibility” means there is evidence to suggest a causal relationship between the drug and the AE. A SAR implies a lesser degree of certainty about causality than adverse reaction, which means any AE caused by a drug.

Unexpected: An AE or SAR is considered "unexpected" if it is not listed in the Investigator’s Brochure or is not listed at the specificity or severity that has been observed; or, if an Investigator’s Brochure is not required or available, is not consistent with the risk information described in the general investigational plan or elsewhere in the current application.

Life-threatening: An AE or SAR is considered “life-threatening” if, in the view of either the Investigator or sponsor, its occurrence places the patient or subject at immediate risk of death. It does not include an AE or suspected adverse reaction that, had it occurred in a more severe form, might have caused death.

NOTE: Events that are related and expected due to uncomplicated cataract surgery should not be classified as an AE.

A **SERIOUS ADVERSE EVENT (SAE)** is any AE or suspected adverse reaction occurring at any dose that:

- Results in death.
- Is life-threatening.
- Results in a persistent or significant incapacity or substantial disruption of the ability to conduct normal life functions.
- Requires inpatient hospitalization.
- Prolongs inpatient hospitalization.
- Is a congenital anomaly/birth defect.
- Is a significant medical event (i.e., one that may jeopardize the subject or may require intervention to prevent one or more of the other outcomes listed above).

A **NON-SERIOUS ADVERSE EVENT** is any AE that does not meet the definitions for SAEs as described above.

Each AE will be classified as **SERIOUS or NON-SERIOUS** using the definitions provided above.

The **SEVERITY** of each AE will be classified as **MILD, MODERATE, or SEVERE**.

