9. STATISTICS

9.1. STATISTICAL METHODS

Continuous measures (e.g., age) will be summarized descriptively by the mean, standard deviation, median, minimum and maximum values. Categorical measures will be summarized by the number and percent of subjects.

If the two placebo groups demonstrate no statistically significant difference, they will be pooled for analysis.

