9.2. SAMPLE SIZE ESTIMATION

A two group chi-squared test with a 0.05 two-sided significance level will have 91% power to detect the difference between a proportion of responders in either of the active dosing regimen groups of 0.31 and a combined placebo group proportion of 0.14 when the sample size in each group is 134.

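### As supplied, Section 9 commits to neither change in IOP from baseline nor a by-arm count of study eyes with a pressure rise, so a rise in a minority of eyes would be diluted in the planned summary

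*Combined protocol and SAP*

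**What the plan says.** All references are to the combined protocol and SAP.

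- **Objectives (2.1, 2.2).** Safety against placebo is part of the primary objective. Comparative safety of the two strengths and regimens is part of the secondary one.
- **Collection (Appendices 1 and 5).** IOP is taken at Visit 1 and Visits 3 to 7. Section 5.1.3 has ocular assessments done in each eye at Visit 3.
- **Entry limit (4.2, 4.3).** A history of glaucoma, or IOP above 21 mmHg at screening or randomization, excludes the subject. This is the only IOP cut-off in the documents.
- **Endpoint (3.1.2.1).** IOP is listed as a measurement only. Change from baseline is specified for palpebral erythema, corneal edema, hyphema, ciliary flush and bulbar injection.
- **Analysis (9.1.3, 9.1).** "IOP measurements, Snellen Distance VA by pinhole method and Slit Lamp Biomicroscopy will be summarized as safety outcomes". Continuous measures "will be summarized descriptively by the mean, standard deviation, median, minimum and maximum values". The single-study-eye rule in 9.1.2 is written for efficacy measures; 9.1.3 does not say which eye's IOP is summarised.
- **AEs (8.2, 8.3, 9.1.3).** An AE is "Any untoward medical occurrence associated with the use of an investigational product in humans, whether or not considered drug related". A note then says: "Events that are related and expected due to uncomplicated cataract surgery should not be classified as an AE". Sections 5.1.2, 5.1.3 and 8.3 repeat the exclusion. None lists the expected changes, and none mentions IOP. AEs that are recorded are tabulated by study group.

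**The concern.** An arm-level mean or median responds weakly to a change confined to a few eyes. The documents do not say what form a pressure effect would take. If it were a sizeable rise in a small fraction of eyes, most of the planned statistics would barely move, and the one that would move clearly, the maximum, describes a single eye. The natural summary for that pattern is a count of eyes per arm, and the plan does not commit to one.

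The AE table might be expected to supply the count. It does so only if each pressure rise is recorded as an AE, and that depends on how each site reads the undefined term *expected*.

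At stake is how well the trial answers its own safety objectives. Efficacy conclusions are not affected. If no threshold is fixed in advance, any count produced later is also open to the criticism that the cut-off was chosen after seeing the data.

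**Working it through.** **Step 1. The plan's own figure.** Section 9.2 gives no safety calculation. Its efficacy statement is "A two group chi-squared test with a 0.05 two-sided significance level will have 91% power" for "active dosing regimen groups of 0.31 and a combined placebo group proportion of 0.14 when the sample size in each group is 134". With mean proportion (0.14 + 0.31)/2 = 0.225:

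- z = [0.17 × √134 − 1.96 × √(2 × 0.225 × 0.775)] / √(0.14 × 0.86 + 0.31 × 0.69)
- = (1.968 − 1.157) / 0.578 = 1.40, so power = 0.919.

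The stated 91% is reproduced to within a point. The "approximate 2:2:1:1 ratio" of 402 subjects gives 134, 134, 67 and 67, so a comparison of 134 with 134 requires the placebo groups to be pooled.

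**Step 2. Dilution of the mean.** The documents give no rate, size or SD for IOP, so these are assumptions: 5% of active eyes rise by 12 mmHg, the rest are unchanged, no placebo eyes rise, and the SD of unaffected readings is 3 to 4 mmHg.

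- Eyes affected: 0.05 × 134 = 6.7.
- Shift in the arm mean: 0.05 × 12 = 0.6 mmHg.
- Standard error (SE) with the same SD in both arms: SD × √(2/134) = 0.37 (SD 3) to 0.49 (SD 4).
- The affected eyes add variance 12² × 0.05 × 0.95 = 6.84. The active-arm SD becomes √(9 + 6.84) = 3.98 or √(16 + 6.84) = 4.78.
- SE then: √[(15.84 + 9)/134] = 0.43 to √[(22.84 + 16)/134] = 0.54.

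The shift is 0.6/0.54 = 1.1 to 0.6/0.43 = 1.4 standard errors. At 3% of eyes and 10 mmHg it is 0.3 mmHg, below one standard error.

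**Step 3. Mean against count.** Power at two-sided 0.05 is used here only as a yardstick, since Section 9.3 makes all other p-values descriptive. Assumptions: a 10 mmHg rise, SD 3 to 5 mmHg, 134 per group. Means use a normal approximation that includes the added variance; counts use Fisher's exact test.

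| Eyes with a rise, active v placebo | Expected eyes | Mean difference (mmHg) | Power, means | Power, counts |
|---|---|---|---|---|
| 3% v 1% | 4.0 v 1.3 | 0.2 | 5–7% | 8% |
| 5% v 1% | 6.7 v 1.3 | 0.4 | 9–16% | 34% |
| 10% v 1% | 13.4 v 1.3 | 0.9 | 27–50% | 90% |

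**Step 4. What the maximum shows.** The chance that an arm of 134 holds at least one affected eye is 1 − 0.95^134 = 99.9% at a 5% rate and 1 − 0.99^134 = 74% at 1%. The maximum would therefore nearly always reveal a rise in the 5% arm. It would often reveal one in the 1% arm too, so two arms with a fivefold difference in rate can show similar maxima.

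**Step 5. The AE route.** The definition in 8.2 covers events whatever their relation to drug. The note removes events that are both related to and expected from uncomplicated surgery. The only condition named as outside AE capture is inflammation due to surgery (5.1.3, 8.3). For IOP the text is silent in both directions, so inclusion in the AE table is neither ruled out nor assured.

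**The case against.** Much of the case on the other side stands.

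- **A reader might infer that a pressure rise could vanish from the arm comparison.** The documents do not support that. IOP is recorded at Visits 3 to 7 whatever the AE decision, and the maximum and SD are planned. In Step 2 the active-arm SD goes from 3 to 3.98, which is visible. Eyes above 21 mmHg on Day 1 are not eligible, so, deviations aside, a later maximum above 21 in an eligible eye is new since Day 1.
- **A reader might infer that the AE note excludes pressure rises.** No section calls an IOP rise an expected surgical change. The fault is an undefined term. Nor do the documents say that a masked investigator cannot tell a surgical rise from a drug-related one, and nothing here rests on that.
- **Descriptive safety reporting is not itself an error.** What is missing is the change and count summaries.
- **The count has limited sensitivity.** At 3% v 1% it does little better than the mean.
- **IOP-lowering treatment would be identifiable**, because Section 6.2 records every medication with dates and indication. The plan does not say how pressures recorded after such treatment are to be summarised.
- **A fuller plan may exist.** Section 9.5 mentions a statistical analysis plan, but nothing beyond Section 9 is supplied.

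None of this supplies the by-arm number of affected eyes.

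**Conclusion.** The point holds in a limited form. In the supplied text, IOP is reported by general summary statistics only, change from baseline is not specified for it, and no planned output is certain to give the number of study eyes with a pressure rise in each arm. A rise in a minority of eyes would be diluted in the mean and median. The maximum would signal it without sizing it, and the AE table may or may not capture it.

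On assumed inputs the dilution is to 0.6 mmHg against an SE of about 0.4 to 0.5. The gain from counting is material at 5% v 1% (34% against 9–16%) and large at 10% v 1% (90% against 27–50%), but negligible at 3% v 1%. The rates, rise sizes and SDs are illustrative, and the calculations assume pooled placebo.

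This is an inexpensive improvement to the safety analysis. It does not show that the trial would miss a pressure effect, and the efficacy power is untouched. It covers the supplied text only.

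**What to change.** In Section 9.1.3 add one table, for study eyes, by arm:

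1. Change in IOP from Visit 3 (the baseline named in Section 9.6) at each of Visits 4 to 7.
2. The number and percent of eyes that, at any post-baseline visit, have (a) IOP above 21 mmHg, the protocol's own entry limit, or (b) a rise above a threshold that the sponsor sets before unmasking. Report (a) and (b) separately, with a confidence interval for each active-minus-placebo difference.
3. A flag on values recorded after any IOP-lowering medication, taken from the concomitant medication data in Section 6.2.

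In Section 8.2, state whether IOP rises after the first dose fall under expected surgical events, and reconcile Sections 5.1.2, 5.1.3 and 8.3 with that statement.

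The cost is one table from data already collected and one sentence in 8.2. No visit, sample-size or alpha change is needed. The limitation to state alongside the table is that 134 per arm (67 per placebo group if not pooled) is informative mainly for fairly large differences, so a similar count in the arms should not be read as absence of an effect.

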9.2. SAMPLE SIZE ESTIMATION

A two group chi-squared test with a 0.05 two-sided significance level will have 91% power to detect the difference between a proportion of responders in either of the active dosing regimen groups of 0.31 and a combined placebo group proportion of 0.14 when the sample size in each group is 134.

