4.4. SUBJECT WITHDRAWAL CRITERIA

Any subject who wishes to withdraw from the study on his or her own accord for any reason is entitled to do so without obligation. The Investigator may remove any subject from the study, if it is deemed necessary.

Any subjects not responding adequately to the study medication may be rescued and placed on alternate therapy at the Investigator's discretion at any time. The subject should remain in the study and continue to be evaluated at the regularly scheduled visits. In the event study discontinuation of a randomized subject is necessary, the Investigator should make every attempt to have subject complete Visit 6 assessments and/or follow through until Investigator deems the reason for study discontinuation has resolved, if applicable. If a non-serious adverse event (AE) is unresolved at the time of the subject's final study visit, an effort will be made to follow up until the AE is resolved or stabilized, the subject is lost to follow-up, or there is some other resolution of the event. The Investigator should make every attempt to follow all serious adverse events (SAEs) to resolution.

Subjects who withdraw from the study will not be replaced.

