9.1.2. Analysis of Efficacy

The primary analysis population will be the Intent-to-Treat (ITT) population, defined as all subjects randomized. A subset of efficacy analyses will be examined for the Efficacy Evaluable (EE) population defined as all subjects who were randomized, completed 14 days of study product use, had complete data at the Day 8 visit and did not have significant protocol deviations.

The primary analysis of all ophthalmic efficacy measures will be based on a single study eye for each subject. Each subject's study eye will be defined as the surgery eye.

The set of primary endpoints, using hierarchical statistical testing, is (1) the difference in the proportion of study eyes with complete resolution of anterior chamber cells (grade = 0) at postoperative Day 8 maintained through end of study and no need for rescue medication for KPI-121 0.25% QID compared to placebo; (2) the difference in the proportion of study eyes with complete resolution of anterior chamber cells (grade = 0) at postoperative Day 8 maintained through end of study and no need for rescue medication for KPI-121 1.0% BID compared to placebo;; (3) the difference in the proportion of study eyes with complete resolution of pain (grade = 0) at postoperative Day 8 maintained through end of study and no need for rescue medication for KPI-121 1.0% BID compared to placebo; and (4) the difference in the proportion of study eyes with complete resolution of pain (grade=0) at postoperative Day 8 maintained through end of study and no need for rescue medication for KPI-121 0.25% QID compared to placebo.

The following scoring scale for anterior chamber cells will be used:

- 0 = No cells seen
- 1 = 1 - 5 cells
- 2 = 6 - 15 cells
- 3 = 16 - 30 cells
- 4 = greater than 30 cells

The following scoring scale for ocular pain will be used:

- 0 = None
- 1 = Minimal
- 2 = Mild
- 3 = Moderate
- 4 = Moderately Severe
- 5 = Severe

If the two placebo groups demonstrate no statistically significant difference, they will be pooled for analysis.

Using the hierarchical testing scheme, the first test will be the difference in the proportion of study eyes with complete resolution of **anterior chamber cells** (grade = 0) at postoperative Day 8 between the pooled placebo control group and the KPI-121 0.25% QID group using the chi-squared statistic.

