If this test is statistically significant at the two-sided $\alpha = 0.05$ level in favor of the KPI-121 0.25% QID group, then the difference in the proportion of study eyes with complete resolution of **anterior chamber cells** (grade = 0) at postoperative Day 8 between the pooled placebo control group and the KPI-121 1.0% BID group will be tested using the same statistic.

If this test is statistically significant at the two-sided $\alpha = 0.05$ level in favor of the KPI-121 1.0% BID group, then the difference in the proportion of study eyes with complete resolution of **pain** (grade = 0) at postoperative Day 8 between the pooled placebo control group and the KPI-121 1.0% BID group will be tested using the same statistic.

If this test is statistically significant at the two-sided $\alpha = 0.05$ level in favor of the KPI-121 1.0% BID group, then the difference in the proportion of study eyes with complete resolution of **pain** (grade = 0) at postoperative Day 8 between the pooled placebo control group and the KPI-121 0.25% QID group will be tested using the same statistic.

Secondary endpoints will be the proportion of study eyes with complete resolution (grade = 0) of anterior chamber cells (scale 0-4) and complete resolution (grade = 0) of pain (scale 0-5) at Day 8 and at Day 15.

Additional secondary endpoints are composite mean scores of anterior chamber cell and pain grades which will be summarized for each study group at each visit.

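### Does it matter that Section 9.2 never says which primary endpoint its response rates of 0.31 and 0.14 describe?

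*Combined protocol and SAP*

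**What the plan says.** Section 9.2 is a single sentence. For a chi-squared test at two-sided 0.05 it claims "91% power to detect the difference between a proportion of responders in either of the active dosing regimen groups of 0.31", against 0.14 in the combined placebo group, at 134 per group. Neither the term responder nor the two rates appear elsewhere, and no source is given.

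Section 9.1.2 lists four primary tests in a fixed sequence. Tests 1 and 2 concern anterior chamber cells, and tests 3 and 4 concern pain. In that list, success in test 1 means clearing "at postoperative Day 8 maintained through end of study and no need for rescue medication for KPI-121 0.25% QID compared to placebo". The pain tests carry the same conditions: "the difference in the proportion of study eyes with complete resolution of pain (grade = 0) at postoperative Day 8 maintained through end of study", again without rescue. The Synopsis and Section 3.1.1.1 give the same four definitions.

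Later in Section 9.1.2, the sentences that set out the order of testing are shorter. The first compares the proportions cleared "at postoperative Day 8 between the pooled placebo control group and the KPI-121 0.25% QID group using the chi-squared statistic", and does not repeat the maintenance and rescue conditions. The three sentences that follow are worded in the same way.

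Section 8.5 says that rescued subjects count as treatment failures. Section 3.2.1 plans for "up to 402 subjects with one study eye each randomized in this study", allocated about 2:2:1:1.

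**The concern.** A sample size can be checked only against a named endpoint. Here the rates could describe cells or pain, and either the sustained rescue-free outcome or clearing at Day 8 alone.

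Two things seemed to be at stake. First, if the rates are for clearing at Day 8 alone, some responders could later relapse or need rescue, and power for the sustained endpoint would not be 91%. Second, if the rates are for cells only, Section 9.2 gives no sizing basis for the pain tests, which are also primary. The reverse holds if they are for pain only.

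The section also gives power for one comparison only, although each test after the first is reached only if the one before it succeeds.

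**Working it through.** **1. Reproduce the stated power.** Inputs from Section 9.2: p1 = 0.31, p0 = 0.14, n = 134 per group, two-sided alpha 0.05 (z = 1.960). The group size agrees with Section 3.2.1: 402 × 2/6 = 134 per active group, and the two placebo groups together also make 134.

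- Pooled proportion: (0.31 + 0.14)/2 = 0.225
- Standard error under the null: √(2 × 0.225 × 0.775/134) = 0.05102
- Standard error under the alternative: √[(0.31 × 0.69 + 0.14 × 0.86)/134] = 0.04995
- Power = Φ[(0.17 − 1.960 × 0.05102)/0.04995] = Φ(1.402) = 0.919

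Exact enumeration over two binomials, with the uncorrected Pearson chi-squared test in favour of active, gives 0.925. With a continuity correction the approximation gives 0.895. The stated 91% is sound as the power of one pairwise test.

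**2. Compare Section 9.2 with the four tests in Section 9.1.2.**

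| Element | Section 9.2 | Section 9.1.2, tests 1 to 4 | Match |
|---|---|---|---|
| Test | two-group chi-squared | chi-squared throughout | yes |
| Alpha | two-sided 0.05 | two-sided 0.05 at each step | yes |
| Active arm | either regimen | 0.25% QID or 1.0% BID | yes |
| Comparator | combined placebo | pooled placebo | yes |
| Endpoint | not named | cells (1, 2), pain (3, 4) | open |

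Only the endpoint is open.

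**3. How much could the success definition matter?** Suppose 0.31 and 0.14 are rates at Day 8 alone, and a share of responders is later lost to relapse or rescue. The documents give no such shares, so those below are assumptions. Each rate is the Day 8 rate times (1 − loss), for example 0.31 × 0.90 = 0.279. Power is for one test at 134 per group.

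| Loss, active / placebo | Rates | Normal approx. | Exact |
|---|---|---|---|
| none | 0.310 vs 0.140 | 91.9% | 92.5% |
| 10% / 10% | 0.279 vs 0.126 | 88.1% | 88.8% |
| 20% / 20% | 0.248 vs 0.112 | 83.0% | 83.8% |
| 10% / 20% | 0.279 vs 0.112 | 93.6% | 94.2% |
| 20% / 40% | 0.248 vs 0.084 | 95.4% | 96.1% |
| 20% / 10% | 0.248 vs 0.126 | 72.9% | 73.6% |

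The results fall on both sides of 91%. Equal loss, or more loss on active, lowers power. More loss on placebo raises it in the cases shown. If the rates already describe the sustained, rescue-free outcome, the first row applies and the stated figure stands.

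**4. Cells or pain.** If the 17-point difference held at a higher placebo rate (also an assumption), the approximation gives 87.3% for 0.37 vs 0.20, 82.0% for 0.47 vs 0.30 and 79.9% for 0.57 vs 0.40. So one pair of rates need not serve both signs. The documents give no rate from which to judge whether pain would differ.

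**5. Does any of this reach the analysis?** The response rates assumed in Section 9.2 enter no test statistic, decision rule or missing-data step in Sections 9.1.2, 9.3 and 9.4. The endpoints to be analysed are defined in Sections 3.1.1.1 and 9.1.2 without reference to the word responder. Defining it in Section 9.2 would leave every planned result as it is.

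**The case for a change.** The best case for a change is that the clarification costs a sentence or two and makes the sizing checkable. The natural reading is that the rates belong to test 1: cells, sustained, without rescue. Nothing in the documents says so, and if it is right, the pain tests have no stated power. There is also little slack, since 402/3 is exactly 134 and "Subjects who withdraw from the study will not be replaced". Finally, each later test depends on those before it. If both active groups truly respond at 0.31 on cells, with pooled placebos and no missing data, exact enumeration gives an 87.0% chance of winning tests 1 and 2, against 92.5% for one.

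It stands that the endpoint and the source of the rates are unnamed, and that stating them would help a reader. The rest does not carry the point further. Sizing on the first test of a fixed sequence is a legitimate choice, and the plan never claims power for winning two or more tests together. The 5.5-point cost (92.5% − 87.0%) is an ordinary consequence of sequential testing. The question of withdrawals is separate from what a responder is. The shorter wording of the test sentences in Section 9.1.2 concerns the endpoint definition itself, and changing Section 9.2 would not resolve it. It follows directly on the full list and can be read as shorthand for it.

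**Conclusion.** The observation is correct, but it is a gap in the design justification that a statistician fills sensibly. The 91% is right as pairwise power (91.9% approximate, 92.5% exact), and every element of the calculation other than the endpoint matches the primary tests. The sustained, rescue-free definition is given in the Synopsis, Section 3.1.1.1 and the endpoint list of Section 9.1.2, and Section 8.5 already treats rescue as failure. That makes it the better-supported reading of responder, and under it the stated power stands.

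The alternative reading moves single-test power to between 73.6% and 96.1%, but only under assumed losses, and the range lies on both sides of the stated figure. It therefore establishes neither a shortfall nor a direction. Sample size, alpha, test order and analysis all stay as planned, and no result or conclusion would differ if the definition were written in.
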